### Study Sessions

All participants will be required to have a BAC of 0.02% or less to complete study sessions. Following screening, subjects will receive either ZON or drug placebo (and TC) for 12 weeks, followed by a 2 week taper off medication. Most weekly study sessions will be approximately 45-60 minutes in duration. Session 1 will be approximately 3 hours, while session 12 will be approximately 2 hours in duration. Follow-up data will be collected at the end of the drug taper (week 14) and then again two weeks later (at study week 16). We will allow up to four weeks for completion of this week 16 follow-up phone assessment. Therefore, participants will have a 20-

week window to complete all study procedures before their participation is considered complete. Assessments that will be obtained during the course of the study are shown in Table 1.

We will ask participants to schedule a standing appointment for each week of the 14-week study, with each appointment scheduled 7 days apart. However, we will allow participants to reschedule an appointment between 7-10 days after their previous session if necessary. The length of time until the subsequent session would then be modified in an attempt to re-establish the original schedule. If a session is scheduled beyond this 7-10 day window (i.e., days 11-14), the session will still be conducted but will be considered the next session. The prior session will be considered “missed.” Participants who miss two consecutive sessions during any 14-day period will be tapered off the study medication and withdrawn from the trial for safety reasons. Participants who are withdrawn will be asked to return weekly to complete the medication taper.

*Interventions:*

Medication treatment (Zonisamide vs. placebo) and Take Control will be administered using a double-blind procedure to subjects during scheduled visits over a period of 14 weeks.

I. Zonisamide (ZON):

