All medication records and dispensing will be managed by the nurse administrator. Pills will match the placebo. Based on previous findings (Knapp et al., 2015), ZON dose of 400 mg daily will be used as the target maintenance dose in this study. A final target maintenance ZON dose of 400 mg will be given after a seven week long titration period. Based on the known half-life of ZON, it is expected that it will take approximately 2 weeks to reach steady state for a given dose of ZON. Participants will begin the medication taper schedule at week 12. According to this schedule, participants will be reduced to a dosage of 300 mg for the entirety of week 12, reduced to a dosage of 200 mg for the first three days of week 13, reduced to a dosage of 100 mg for the next three days, and then the participant will be done taking the medication. Therefore, the participant will be completely off of the medication by the day before the week 14 session. Pill placebo will be administered according to the Zonisamide schedule.

Dosage escalation and maintenance regimen

Week 1 + 2	Week 3 + 4	Week 5 + 6	Week 7 – 12 Maintenance
100 mg/day (once a day)	200 mg/day (once a day)	300 mg/day (once a day)	400 mg/day (once a day or two divided doses)

Dosing will be modified, if needed, to adjust for subject tolerance of drug dosing or to reduce adverse drug effects. Verification of medication adherence compliance will entail comparing the patient’s self-report against the number of pills remaining in the medication vial. Pill counts will be conducted at each visit to encourage medication adherence.

Medication will be dispensed according to a two-week dosing schedule by medical personnel at weekly study sessions. Participants will be supplied with two medication bottles at each study visit, containing between 4-7 days of medication in one bottle and 7 days of medication in the other. At any given time, participants may have between 10-17 days of medication in two or three medication bottles. Patients will self-administer medications daily, as directed.

Patients who have to discontinue medication will be permitted to remain in the study and participate in study assessments and will be allowed to continue to receive TC.

Participants who are withdrawn from the study will be tapered off the medication. Any unused medication can be returned during the taper period, either in person or by a postage-paid return envelope we will supply them with.

II. Take Control:

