CONN creates subject-specific ROI files and registers them to the subject space. 99 ROIs will be used as the seeds of interest for whole-brain subject-specific ROI-ROI connectivity analyses.

**Power Analysis:** Power analysis for drinks consumed per day during the last three weeks of treatment were determined using data for the placebo and zonisamide groups from our previous study (Knapp et al., 2015). A power value of 0.9 was found for a group size of 40, with alpha=0.05, and with an effect size of 0.74. In our previous study of ZON approximately 20% of subjects dropped out before week 12 of the study. Consequently, we will randomize 50 subjects per group to reach a target of 40 subjects in week 12 of the present study. Based on data reported by Rubio et al. (2009) for errors of commission on the CPT, a measure of impulsivity, a power value of 0.97 would be obtained for an alpha value of 0.05 for a group size of 40. Based on the findings of Myrick et al., (2008) for the difference between the activation of the ventral striatum for placebo and naltrexone groups a power of 0.88 was seen for an effect size of 0.7 for a group size of 40.

**Safety Analysis:** For safety, subjects will be assessed as having had any serious adverse event during the treatment period or not, and additional analyses will be done by separate types of adverse events. Tolerability will be assessed as a subject being able to continue on the study drug for the entire study duration without requiring discontinuation. The safety and tolerability of the study medications will be first assessed using contingency tables and chi-square tests. Fisher's exact test will be employed for rare adverse events. The chi-square analysis will be followed by logistic regression analyses, adjusting for the stratification factor. Time to drug discontinuation for serious adverse events and time to withdrawal from the study for any reason will be assessed using Kaplan-Meier survival curves and compared between study treatments using the log rank test. Poisson regression will be used to evaluate the rate of serious adverse events by arm stratified by the time periods of dosage escalation, dosage maintenance, and dosage taper.

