#### Potential side effects of Zonisamide

The most common adverse reactions associated with ZON administration in seizure patients include: somnolence (17%), dizziness (13%), and anorexia (13%). Less common adverse effects include: agitation (9%), irritability (9%), depression (6%), speech abnormalities (5%), confusion (6%), difficulty with concentration (6%), difficulty with memory (6%), fatigue (8%), insomnia (6%), nausea (9%), and headache (10%). In some patients, ZON can contribute to problems with concentration, attention, memory, mood, thinking, speech, or language. ZON may produce urinary lithiasis [Kubota et al., 2000]. The incidence of this is reported to be 1.9% in clinical trials in the United States and 0.2% in Japanese clinical trials. The risk of urinary stone formation may be higher in dehydrated and bedridden patients.

Acute myopia and secondary angle closure glaucoma have been reported in patients receiving ZON. Symptoms in reported cases have included acute onset of decreased visual acuity and/or ocular pain. Symptoms typically occur within one month after initiating ZON therapy.

Zonisimaide can cause metabolic acidosis, which results in high levels of acid in the body. If untreated, metabolic acidosis can lead to kidney stones or soft bones. Kidney stones can also occur while taking ZON in the absence of metabolic acidosis. The rate of occurrence for kidney stones is 28.7 per 1000 patient-years of exposure in the first six months, 62.6 per 1000 patient-years of exposure between 6 and 12 months, and 24.3 per 1000 patient years of exposure after 12 months of use (Food & Drug Administration (FDA), 2020).

Other rare but potentially life threatening side effects include allergic reactions that may affect different parts of the body, cause blood cell changes such as reduced white blood cells counts, or lead to a serious skin rash such as Stevens-Johnson Syndrome (SJS) or Toxic Epidermal Necrolysis (TEN). SJS and TEN are two forms of the same life-threatening skin disease that cause rash, skin peeling, and sores on the mucous membranes.

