**Risk of loss of confidentiality**

The investigator and his staff will take every precaution to maintain subject confidentiality; however, there is always the possibility that confidentiality may be broken.

**Describe the plan to minimize risks. Include in the description the availability of any medical or psychological resources.**

The overriding concern of the investigators is the safety of the subjects who participate in this study. Participants will be informed about all risks and told that they may withdraw from the study at any time and may refuse to complete any treatment procedures. Study personnel will be monitoring the patients' clinical condition carefully and constantly and will withdraw patients from the study if their clinical condition warrants.

In order to minimize risks, patients with prominent suicidal ideation (assessed as part of the clinical interviews, including the MINI, and with the self-monitoring forms) will be excluded. Treatment will be closely monitored by the PI in weekly supervision meetings. The MINI Suicidality interview will be used to measure participants' suicidality scores during the screening session, and will be administered to measure suicidality at every session during clinic visits, and at follow up by phone. A significant increase in depression is defined by scoring at least 10 points higher than baseline on the BDI-II, and getting a total scoring of at least 17. Clinical judgement by the study physician or associated licensed psychologist will be used to decide whether a suicidal potential has developed. The clinical case of any patient showing significant increases in depression symptoms or developing suicidal potential will be reviewed by the PI. These patients will be asked to withdraw from the protocol and given or referred to immediate clinical intervention. Appropriate protective factors and safety plan will be followed based on the attached document, if the patient reports suicidal thoughts with high levels of intent

with a specific plan/access, or regardless of plan. Additionally, all patients will be clearly informed of their right to withdraw from the study at any point.

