#### Zonisamide

In order to minimize potential side effects of ZON, subjects who can be expected to experience any severe side effects will be excluded from the study by the screening procedures. Laboratory values for relevant blood chemistry will be collected at screening and approximately every two weeks during the acute treatment period. Treatment will be discontinued under the authority of the study physician if there is evidence of metabolic acidosis, acute renal injury ( $>3$ fold increase in serum creatinine levels from baseline) or a significant change in liver function (AST or ALT  $> 3$ X UNL for more than two weeks). A physician will be available on-call at all times to answer medical questions or to assess subjects for potential medical problems or untoward effects due to their participation in the study. In addition, participants will carry an alert card on their person, explaining the effects of the study medications and a 24-hour phone number to call, in case of emergency. Should a subject experience a severe adverse drug reaction, they will receive an evaluation by a physician. Symptoms may become severe enough to require hospitalization in order to be managed safely and assistance with withdrawal will be readily available during all phases of treatment. If management of withdrawal is necessary, subjects will be evaluated and treated at a local emergency facility. However, no special provision will be made for compensation or for payment for treatment solely because of their participation in this study.

The dosage regimen selected for the administration of Zonisamide in this study (target maintenance dose of 400 mg per day) was selected based on our experience with this drug in treating alcohol-dependent subjects. The Take Control alcohol reduction and medication compliance program has been tested in one of our completed multisite clinical trial and is currently being used in a second NIAAA sponsored multisite medication trial.

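### Participants who develop suicidal potential are asked to leave the protocol, not only to stop the drug, and the available text plans no contact with them after the taper

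*Combined protocol and SAP*

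**What the plan says.** **The exit rule.** Section M (plan to minimize risks) schedules the MINI Suicidality interview at every session and at the follow-up call. It defines a significant depression increase as a BDI-II score at least 10 points above baseline with a total of at least 17. The principal investigator reviews any participant with such an increase or with suicidal potential, and then: "These patients will be asked to withdraw from the protocol and given or referred to immediate clinical intervention". A safety plan is attached to the application.

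**The rule for other drug stops.** Section L (Zonisamide) states: "Patients who have to discontinue medication will be permitted to remain in the study and participate in study assessments". Laboratory findings are handled as drug stops. Section M (Zonisamide) says "Treatment will be discontinued under the authority of the study physician if there is evidence of metabolic acidosis", and treats acute renal injury and liver changes the same way.

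**What withdrawn participants are offered.** Section L (Study Sessions), in its missed-session rule, says: "Participants who are withdrawn will be asked to return weekly to complete the medication taper". The Zonisamide subsection also gives withdrawn participants a taper and nothing more. The Overview ties the week-16 call to completion of study treatment.

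**Why mood events may be drug-related.** Section M notes that in some patients "ZON can contribute to problems with concentration, attention, memory, mood, thinking, speech, or language". It lists depression (6%), agitation (9%) and irritability (9%) among adverse reactions in seizure patients.

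**How safety is analysed.** In the Safety Analysis, "subjects will be assessed as having had any serious adverse event during the treatment period or not". It also covers tolerability, "Time to drug discontinuation for serious adverse events and time to withdrawal from the study for any reason", and a Poisson regression of serious-event rates by arm and dosing period. The DSMB receives yearly reports of retention and reasons for dropout by arm (Section R).

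**The concern.** The two rules treat drug stops differently, and no reason is given. A participant who stops for acidosis can stay under observation. One who develops suicidal potential is asked to leave, although the protocol itself names mood among the drug's possible effects and watches suicidality at every session. Planned observation of that signal therefore ends when the signal appears. Clinical referral protects the patient but returns no outcome to the trial.

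Two analyses are touched. The serious-event comparison depends on hearing about events. After the taper no contact is planned that would detect one, so it would be learned of by chance. Section R requires the outcome of a reported serious event but sets no visits to find new ones. The drinking comparison (Data Analysis, aim 4) uses a repeated-measures mixed model over the 12 treatment weeks, and an early leaver contributes an incomplete record. If such exits are more common in one arm, the missing data are related to treatment.

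**Working it through.** **1. When each trigger can act.** Table 1 schedules the MINI at every session, so suicidal potential can be found at any week. It schedules the BDI-II only at about weeks 1 and 12. Week 1 is baseline, so a rise can be detected only at about week 12.

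**2. Length of the taper.** From 400 mg, Section L gives 300 mg for 7 days, 200 mg for 3 and 100 mg for 3: 7 + 3 + 3 = 13 days, about two weekly visits. From the week-4 dose of 200 mg the same steps take at most 3 + 3 = 6 days, about one visit. The documents do not say which assessments are done at these visits. I therefore bracket the loss between full assessment at two taper visits and none.

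**3. MINI contacts lost per exit.** After baseline there are 13 contacts in weeks 2 to 14 plus the week-16 call, 14 in all. An exit at week w keeps weeks 2 to w (no taper assessment) or 2 to w + 2 (both visits).

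**4. Treatment weeks without TLFB, of 12.** The loss is 12 − w with no taper assessment, or 12 − (w + 2), not below zero, with both visits.

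| Exit week | MINI contacts lost, of 14 | TLFB weeks lost, of 12 |
|---|---|---|
| 4 | 14 − 5 = 9 to 14 − 3 = 11 | 6 to 8 |
| 8 | 14 − 9 = 5 to 14 − 7 = 7 | 2 to 4 |
| 12 | 14 − 13 = 1 to 14 − 11 = 3 | 0 |

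With the single taper visit expected at the week-4 dose, a week-4 exit loses 10 MINI contacts. The week-12 row is the BDI-II trigger: it costs no treatment weeks of drinking data.

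**5. Power.** The plan states power 0.9 for 40 per group, effect size 0.74 and alpha 0.05. Sidedness is not stated; I assume two-sided. The two-sample t-test has noncentrality 0.74 × √(n₁n₂/(n₁ + n₂)). For 40 v 40 this is 0.74 × √20 = 3.31 and power is 0.905, so the stated figure reproduces. The inflation 40/(1 − 0.20) = 50 per group also reproduces. The documents give no rate for these exits, so the following losses beyond the planned dropout are assumed:

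- 40 v 37 (three extra in one arm): 0.893
- 40 v 35 (five extra in one arm): 0.884
- 35 v 35 (five extra in each arm): 0.863

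The loss of power is small. The issue is missing safety and outcome data, not precision.

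**6. What one late call could recover.** TLFB is retrospective. After a week-4 exit, a call at week 16 must reach back (16 − 4) × 7 = 84 days. The protocol puts 90 days of TLFB at about 10 minutes.

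**The case against.** **The gap is inferred from silence.** This stands. No passage bars follow-up after such an exit, and parts of the text describe the week-16 call for participants generally. Patients are asked to withdraw, so one who declines might stay. The safety-plan attachment and the DSMB charter may contain a rule. A reader might infer that the protocol excludes these participants from follow-up; it does not say that. It only plans none in the available text.

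**Withdrawal may be deliberate and protective.** Moving a suicidal participant from a blinded trial to clinical care is defensible. Missed sessions and detoxification also end participation. But stopping the drug and referral give the protection, and both can be kept while contact continues.

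**Few may be affected.** Screening excludes moderate to high suicide risk, the BDI-II trigger acts only at about week 12, and the plan already allows for about 20% dropout. This limits the size but leaves the gap for an early suicidality exit.

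**The exit is already counted.** It enters tolerability, time to withdrawal and the DSMB dropout reports, and a hospitalization would be a reportable serious event. That captures the exit, not what follows it.

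**Stronger readings the documents do not support.** A reader might infer that unobserved time is scored as free of serious events. The Safety Analysis does not say so, and its Poisson rate analysis could allow for shorter follow-up, although no offset is stated. A reader might infer a calculable bias in the drinking effect. Aim 4 uses a 12-week mixed model that takes in a leaver's observed weeks; the last three weeks serve the power calculation, and a completers-only contrast of those weeks is not the planned comparison. A reader might also count a loss to aim 3, which uses weeks 10 to 12. That model needs the week-12 scan as well, so restoring TLFB alone would not bring the participant back into it.

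**Conclusion.** The concern holds as a gap in planned follow-up that is worth closing because closing it is cheap. Section M's exit rule differs from Section L's rule for other drug stops, and the available text plans nothing beyond the taper for those who leave. An early suicidality exit ends planned MINI, adverse-event and TLFB collection for a possibly drug-related event. At week 4 that is 9 to 11 of 14 MINI contacts and 6 to 8 of 12 treatment weeks of TLFB, assuming zero to two assessed taper visits. A BDI-II exit at week 12 loses 1 to 3 MINI contacts and no treatment weeks. The number of such exits, their balance between arms and the size of any bias cannot be derived. The conclusion rests on the available text being complete on this point; a follow-up rule in the safety-plan attachment or DSMB charter would reduce the point to a cross-reference.

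**What to change.** **Section M.** Keep investigator review, clinical referral and the safety plan. Replace the request to withdraw from the protocol with stopping study drug by taper and an invitation to remain, under the existing Section L provision, for MINI, adverse-event and TLFB contacts through week 16. Make the week-16 call the minimum.

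**Safety Analysis.** Tolerability already counts such a drug stop and needs no change. Time to drug discontinuation now covers serious adverse events only; add these stops as events. Do not count participants who stay for assessments as study withdrawals.

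**DSMB report.** List these drug stops by arm each year, since they would no longer appear as dropouts.

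**Cost.** One wording change, one sentence and one report line. The contacts are already scheduled for other participants, and the Covid-19 section says all sessions are already remote. On the timing of the last call the protocol says: "We will allow up to four weeks for completion of this week 16 follow-up phone assessment". Some participants will decline, and staff must route a positive phone MINI to the safety plan. The change yields suicidality status, adverse-event outcome and drinking data. It does not yield a depression score, because no BDI-II is scheduled after week 12 for anyone.

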#### Alcohol Withdrawal

In order to minimize the possibility of hospitalization during withdrawal, subjects who meet eligibility criteria at the first screening visit will be told that it is unsafe to stop drinking abruptly. They will be educated with respect to symptoms of early and late withdrawal, and be advised to contact the clinic in the event that medically-managed withdrawal may be indicated. A study physician is available by telephone at all times to advise patients concerning withdrawal symptoms or other matters concerning the study. If it is suspected at any time during the study that the subject may be going through withdrawal after a period of heavy drinking and is experiencing withdrawal symptoms that greater than a 10 on the CIWA-AR scale, they will be advised to come to the clinical site for further evaluation, or go directly to an emergency department.

The blind for medication will be kept by the PI and can be accessed 24 hours in case of emergency.

#### Zonisamide

In order to minimize potential side effects of ZON, subjects who can be expected to experience any severe side effects will be excluded from the study by the screening procedures. Laboratory values for relevant blood chemistry will be collected at screening and approximately every two weeks during the acute treatment period. Treatment will be discontinued under the authority of the study physician if there is evidence of metabolic acidosis, acute renal injury ( $>3$ fold increase in serum creatinine levels from baseline) or a significant change in liver function (AST or ALT  $> 3$ X UNL for more than two weeks). A physician will be available on-call at all times to answer medical questions or to assess subjects for potential medical problems or untoward effects due to their participation in the study. In addition, participants will carry an alert card on their person, explaining the effects of the study medications and a 24-hour phone number to call, in case of emergency. Should a subject experience a severe adverse drug reaction, they will receive an evaluation by a physician. Symptoms may become severe enough to require hospitalization in order to be managed safely and assistance with withdrawal will be readily available during all phases of treatment. If management of withdrawal is necessary, subjects will be evaluated and treated at a local emergency facility. However, no special provision will be made for compensation or for payment for treatment solely because of their participation in this study.

The dosage regimen selected for the administration of Zonisamide in this study (target maintenance dose of 400 mg per day) was selected based on our experience with this drug in treating alcohol-dependent subjects. The Take Control alcohol reduction and medication compliance program has been tested in one of our completed multisite clinical trial and is currently being used in a second NIAAA sponsored multisite medication trial.

